6.3 Adverse event monitoring

- Added a comparison of hospitalization rate between arms through 24 months using data compiled from the CDW.

Abstract

1. Objective(s) and Hypotheses:

Our primary aim is to test the effectiveness of a proactively delivered and pragmatic weight loss intervention to improve co-primary endpoints of sleep-related quality of life and weight among Veterans with obstructive sleep apnea (OSA) and obesity. Secondarily, we will compare additional outcomes between groups: cardiovascular risk scores, sleep symptoms, and AHI. Finally, we will also conduct an implementation process evaluation informed by the RE-AIM framework to identify predictors and determinants of population uptake of the intervention, alternative guideline-based treatments for OSA and obesity, and the achievement of patient-centered outcomes.

2. Research Design:

We plan a hybrid type 1 pragmatic randomized controlled trial assessing effectiveness and an implementation process evaluation.

3. Methodology

We will proactively identify Veterans with OSA and obesity nationwide using data from the CDW (n=696), randomizing patients 1:1 to usual care plus the GLB weight loss intervention or usual care alone. We will collect primary outcomes at 12 months, but we will also collect outcomes at 3 and up to 24 months to assess trends over time. We will use quantitative and qualitative methods to assess determinants of implementation of our intervention and other guideline-based treatments for OSA and obesity, budget impact, and maintenance of patient-centered outcomes.

4. Findings/Progress to Date:

Recruitment began on 4/4/2022, analysis has not begun. No interim analysis planned.

5. Relevance to VA Mission

Our research tests a program of proactively providing Veterans with OSA the tools to manage weight loss in a way that is independent of local provider time and resources. Our research addresses a key gap in Veteran's health in a way that aligns with important VA priorities including population health, virtual care, access, and health care value. We anticipate our intervention can efficiently achieve improvements in quality of life while reducing the burden and risk of serious comorbidities.

List of Abbreviations

- Adverse event (AE)
- American Heart Association (AHA)
- Body mass index (BMI)
- Cardiovascular disease (CVD)
- Centers for Disease Control and Prevention (CDC)
- Centers for Medicare and Medicaid Services (CMS)
- Chronic obstructive Pulmonary Disease (COPD)

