OSA.^{24–26} Primary care providers face similar time-pressures that prevent discussions of weight loss.²⁷ As a result, fewer than 1/3 of Veterans with OSA discuss weight loss with providers, and Veterans rarely self-refer to VA's weight loss services (Section 2.5.2-3). Rather than rely on providers whose time is already constrained, weight loss interventions among patients with OSA could benefit from a population health approach that is independent of specialist or primary care providers. Improving access to lifestyle interventions has the potential to expand treatment for OSA and obesity.

2.1.5. VA's current weight loss offerings have poor accessibility, limiting overall effectiveness, particularly among patients with OSA. The behavioral weight loss interventions tested previously in OSA relied heavily on in-person sessions occurring at least once per week—intensity and structure replicated in VA's MOVE! program. While the intensive in-person model may work in clinical trial populations of highly motivated subjects, this format limits reach and effectiveness in the real world. In-person visits are a barrier for the 50% of Veterans who live >30 miles from the nearest facility, and scheduled sessions often conflict with Veterans' work and family obligations.^{28,29} While telehealth options for MOVE! are available, up to 40% of enrolled Veterans do not regularly use the internet.^{30,31} These barriers limit access, and our preliminary data suggest only 12% of Veterans with OSA and obesity engage with any MOVE! services (Section 2.5.2). Poor access also prevents continued attendance. Two-thirds of Veterans attend just 1-3 MOVE! visits leading to limited overall effectiveness.^{31,32} For instance, Veterans with OSA in MOVE! lose just 1.2 kg at one year.³³ Recognizing the limitations of VA's offerings, the National Center for Health Promotion and Prevention (NCP) is interested in integrating new options to improve access, especially programs that are scalable, remote, and capable of reaching those with low tech literacy (See NCP Director [name] LOS). Disseminating accessible weight loss programs will be especially important in OSA. Patients with OSA often require greater engagement with behavioral weight loss programs in order to lose the same weight as peers without OSA,^{33–35} reflecting the need to overcome PAP-related weight gain and metabolic effects of sleep disruption.^{8,9}

[figure not shown]

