Quantifying Costs: Using validated frameworks, we will quantify VA-perspective costs based on A) within-trial costs for implementing the intervention (intervention group only) and B) downstream healthcare utilization (intervention and control).^{76,77} Similar to prior VA studies, study staff will log all time spent monitoring adherence and on general intervention support including 1) lifestyle coach training, 2) individual lifestyle coaching activities (e.g. orientation, responding to ad hoc patient requests), and 3) planning.⁷⁸ Staff time will be converted to costs based on salaries of the staff conducting the intervention using payroll information. Sensitivity analysis will explore alternative staffing models using estimates from US Bureau of Labor Statistics Occupational Outlook Handbook. Time for research-specific activities including consenting and survey assessments will be excluded. All supply and other material costs will be extracted from intervention fidelity tracking data. To assess potential increases or decreases in longitudinal healthcare utilization, we will compare differences in total utilization in the 24-month period following trial enrollment between the intervention and control groups. Healthcare utilization and total payer costs from will be extracted for all encounters using VA's Managerial Cost Accounting data which is an activity-based allocation system based on payroll and all other care-related expenses (eg. supplies, utilities, service contracts) extracted from VA's general ledger, and any claims patients incur for care delivered in the community that is reimbursed by VA. Confidence intervals for any observed differences in healthcare cost between the intervention and control groups will be estimated using bootstrapping, accounting for distributional assumptions for potentially skewed cost data. Costs will be reported in dollars at the time of reporting final results, with earlier years adjusted for inflation using the Consumer Price Index.

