6.0 Reporting

6.1 Quality monitoring

The investigators will closely monitor and prepare annual summary reports on:

- Patient accrual and follow-up completion/retention in relation to goals and timeline.
- Randomization process and group comparability on the balancing variables.
- Key baseline characteristics of the sample, by blinded group, on the primary and secondary outcome variables.
- Intervention adherence.
- Protocol violations.

6.2 Data Safety and Monitoring Board.

This study will be reviewed regularly (at least annually) by a DSMB convened by the national director of VA HSR&D. This board will monitor the quality of data, progress of recruitment, as well as the incidence of adverse events between arms.

6.3.1. Adverse event monitoring.

To ensure unbiased determination across treatment arms, at 12- and 21-month follow-up contact we will ask participants to complete a survey about potential adverse events (AE), serious adverse events (SAE) and unanticipated problems (UP) employing a body system-based assessment. We define SAEs as those requiring hospitalization or death.

Study staff will collect adverse events using participant self-reports collected at 12 and 21 months. Study staff will also perform chart reviews looking for discharge summaries for the 12 month time period. Study staff will later complete additional chart reviews looking for discharge

summaries for the 21 month time period among patients who do not complete 21 month surveys. [name] or another clinician will assess each AE for duration (start and stop dates and times), expectedness in the study population, severity, outcome, treatment, and relation to study activity.

To account for potential differential survey response rates by arm, we will also query the electronic medical record and compile hospital admissions from randomization through 24 months post randomization. We will report the number of hospitalizations by arm to in our final DSMB report.

The following are expected adverse events in the POWER population of participants who have obstructive sleep apnea, a high BMI, and adopt healthy eating and physical activity program:

- Gastrointestinal symptoms related to change in diet.
- Musculoskeletal symptoms or injury resulting from increased physical activity, including increasing symptoms such as chest discomfort, shortness of breath, and leg cramping.

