which models for each patient i their measure for each outcome (FOSQ and weight separately), incorporating time of measurement T_j (0 or 12 months), treatment by time interaction $X_i T_j$, stratification variables Q_i , and adjustment variables A_i including age, gender, race, Charlson comorbidity index, and rurality. The model will include a random normal intercept u_i for each patient and a random normal error term ϵ_{ij} , all assumed independent. The variances of the ϵ_{ij} will be assumed different at baseline and 12 months. Here, β_0 is the average baseline FOSQ/weight among the control and treatment groups combined (assumed equal due to randomization), β_1 is the expected change in FOSQ/weight over time in the control group, and β_2 , the quantity of interest in hypothesis H1, is the expected difference in the change in FOSQ/weight over time between the treatment and control groups, or equivalently the expected difference between groups at 12 months. In secondary analyses, we will incorporate primary and secondary outcomes from each time point (baseline, 3, 12, and 21 months). We will use the same model to test secondary outcomes captured only at follow up, omitting baseline values.

Additional Analytic Subgroups: In addition to analyses of the entire sample using intent to treat, we will analyze primary and secondary outcomes according to model 1 and model 2 in the following groups:

- 1) Subgroups defined by each of the three pre-specified strata (see section 4).
- 2) Subgroups defined by gender.
- 3) Patients who are prescribed continuous positive airway pressure and use <4 hours per night in the 90 days before the outcome period.
- 4) The subgroup of patients who are prescribed continuous positive airway pressure and use ≥ 4 hours per night in the 90 days before the outcome period.

10. Adverse and Serious Adverse Event Monitoring:

To ensure unbiased determination across arms at 12- and 21-month follow-up, we will ask participants to complete a survey about potential adverse events (AE), serious adverse events (SAE) and unanticipated problems (UP) employing a body system-based assessment. We define SAEs as those resulting in hospitalization or death.

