[name] or another licensed independent provider with experience reviewing AEs in clinical trials, [name] ARNP, will assess (using participant self-report and chart review) each AE for duration (start and stop dates and times), expectedness in the study population, severity, outcome, treatment, and relation to study activity for each patient. We will also perform chart reviews at 12 and 21 months to look for discharge summaries within the VA.

The following are expected adverse events in the POWER population of participants who have OSA, a high BMI, and adopt healthy eating and physical activity program:

- Gastrointestinal symptoms related to change in diet
- Musculoskeletal symptoms or injury resulting from increased physical activity, including increasing symptoms such as chest discomfort, shortness of breath, and leg cramping

- Development of weight and OSA associated medical disorders including diabetes, hypertension, liver disease, cardiovascular disease, cerebrovascular disease, arrhythmias, asthma, COPD, clotting problems, and other lung related conditions
- Development or exacerbation of mental health conditions, the worsening of which is known to be associated with poor sleep, including depression, anxiety, posttraumatic stress disorder, and bipolar disorder
- Development or exacerbation of eating disorders including binge eating disorder, anorexia nervosa, and bulimia nervosa.
- Development of other conditions associated with unhealthy health behaviors, such as from tobacco and alcohol disorders (e.g., cancer)
- Age related illnesses, such as pneumonia, urinary tract, and skin infections
- Motor vehicle collision or other accidents arising from excessive sleepiness
- Death

Summary of Edits:

Version 2.0, 11/23/2021

- Minor format changes and typo corrections
- **Section 3. Description of how data will be collected:**
 - Added use of email for recruitment and online questionnaire collection (Qualtrics)
- **Section 4. Method of Randomization:**
 - Removed rural vs. urban strata
 - Redefined physiologic OSA severity strata
 - Added sleep related impairment strata
- Section 10.
 - Added [name] ARNP as additional reviewer of AEs

Version 3.0 2/16/2023

- Minor format changes and clarification that this is a “lifestyle intervention”
- Section 2. Sample Size Rationale

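### Serious adverse events are defined as hospitalization or death, but no stated source systematically searches for deaths, and the 24-month record query does not say whether it covers community admissions

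*Protocol*

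**What the plan says.** **Definition.** Protocol section 6.3.1: "We define SAEs as those requiring hospitalization or death". SAP section 10: "We define SAEs as those resulting in hospitalization or death". Both documents also list death among the expected adverse events.

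**Sources.** Three are named.

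- Surveys of participants at 12 and 21 months (both documents).
- Chart review. In the protocol this looks for discharge summaries for the 12-month period, and for the 21-month period only in participants who did not complete the 21-month survey. The SAP says: "We will also perform chart reviews at 12 and 21 months to look for discharge summaries within the VA".
- A record query, in the protocol only. To allow for survey response that differs by arm, staff will "query the electronic medical record and compile hospital admissions from randomization through 24 months post randomization". The output is stated as: "We will report the number of hospitalizations by arm to in our final DSMB report". The change log for version 2.19 gives the data source: "Added a comparison of hospitalization rate between arms through 24 months using data compiled from the CDW".

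**Reporting.** Under protocol section 6.3.1, SAEs that are both unexpected and related go to the IRB and DSMB on the required timelines. All other events are summarized for the DSMB once a year by number and type, by masked arm.

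**Community care.** For the cost analysis (protocol section 5.5.6.3, Quantifying Costs), utilization over 24 months in both arms includes "any claims patients incur for care delivered in the community that is reimbursed by VA". Section 6.3.1 and SAP section 10 do not mention these claims.

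**The concern.** Death is one of the two limbs of the SAE definition, yet each stated search is built to find something else: a survey answer, a discharge summary or an admission. A death at home or in an accident need not leave any of these. Because death is listed as expected, an ordinary death would normally reach the DSMB through the annual summary, and that summary can contain only what the sources find.

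The 24-month query was added so that the comparison between arms would not depend on who answers surveys. If it counts admissions alone, it leaves out the most serious outcome. If it also misses community admissions, the missing ones are concentrated in survey non-responders, the group for whom the query was added.

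**Working it through.** No figure in the plan depends on this point, so there is nothing to reproduce. The check sets each source against the two limbs of the definition.

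| Source | What it looks for | Out-of-hospital death | Non-VA admission |
|---|---|---|---|
| Surveys, 12 and 21 months | Self-reported events | No; needs a living respondent | Yes, in responders |
| Chart review (protocol) | Discharge summaries; at 21 months, survey non-completers only | Only incidentally | Possible; no VA limit stated |
| Chart review (SAP) | Discharge summaries within the VA, 12 and 21 months | Only incidentally | Not by the stated search |
| Record query (protocol) | Admissions to 24 months | No | Not stated |

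**Step 1: deaths.** The third column has no systematic route. Staff might learn of a death while telephoning about a survey or requesting a missing 12-month weight, but no one is told to check vital status.

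**Step 2: reading the admissions count without vital status.** Someone who dies early out of hospital adds no admission for that death and none afterwards. An arm with more early deaths can therefore show fewer admissions and look safer. The person-time part of this effect can be bounded with assumed mortality:

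- Follow-up: 696 × 2 = 1,392 person-years, or 348 × 2 = 696 per arm.
- Assumed mortality of 0.5% to 1.5% per year: 1,392 × 0.005 = 7 deaths; 1,392 × 0.015 = 21 deaths.
- Extreme case, all deaths in one arm on the day of randomization: 7 × 2 = 14 of 696 person-years (2%), or 21 × 2 = 42 of 696 (6%).

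So lost person-time alone distorts the count little. Participants who die may also be those most often admitted, in which case the share of admissions lost is larger than the share of person-time. The main loss is that the death itself is not counted.

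**Step 3: non-VA admissions.** For responders, the surveys can pick these up. For non-responders, the SAP's chart review does not look for them, and the query's coverage is unstated. Even for responders, an admission between the 21-month survey and month 24 has no self-report route. If survey non-response equalled the planned 20% attrition (protocol section 5.6.1), 696 × 0.20 = 139 participants would have no self-report. Other assumed levels give:

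- 5%: 696 × 0.05 = 35
- 10%: 696 × 0.10 = 70
- 39%: 696 × 0.39 = 271

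These are counts of participants without a survey, not of missed admissions.

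**Step 4: are the data within reach?** VA-reimbursed community claims are planned over the same 24 months in both arms, for costs. The budget impact analysis is conditional on the intervention being effective (sections 5.5.6.3 and 5.6.4), so a safety count should not depend on it.

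**The case against.** Several stronger conclusions are tempting, and the documents do not support them.

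- *That deaths are not reported by arm.* The hospitalization count is one output. Section 6.3.1 also sends all adverse events to the DSMB by masked arm, and death is on the list of events. Known deaths are covered; the weakness is in finding them.
- *That the query is the only safety source independent of survey response.* It is not. The protocol's 12-month chart review has no survey condition, and its 21-month review is aimed at survey non-completers.
- *That community admissions are excluded.* The query is silent on them. The limit to the VA appears only in the SAP and only for chart review.
- *That unequal survey response biases the count of deaths.* Someone who dies before a survey cannot answer it in either arm, so response among the living does not change whether the death is captured. That mechanism applies only to non-VA admissions.
- *That no source could reveal a death.* SAP section 10 has events assessed from self-report and chart review and mentions discharge summaries as an addition, so chart review may be wider. Incidental discovery is possible, but it is not a systematic search.

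Two further points carry weight. The protocol's change log refers to an established DSMB analysis plan and says that a DSMB charter exists. Death ascertainment may be set out there beyond what the supplied SAP says. Safety is also not among the trial's hypotheses, and the SAP describes the intervention as consistent with guideline-based care. These points limit the importance of the gap, but they do not fill it in the two documents reviewed.

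**Conclusion.** The point holds as one of ascertainment. By the stated rules, deaths outside hospital are not actively sought, and the 24-month count by arm covers one limb of a two-limb definition. Whether community admissions are counted is left open, so two analysts following the text could produce different totals.

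The number of missed events cannot be estimated, because the documents give no mortality rate, admission rate or share of care outside the VA. The figures in the working are illustrations under stated assumptions. The entry criteria in section 5.4, which exclude recent hospitalization and short life expectancy, may make true rates lower. The conclusion rests on the wording of the sources and not on those figures.

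The co-primary analyses are unaffected. The change is still worth making: it is cheap, it concerns the most serious outcome, and it supports the purpose the protocol gives for the query.

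**What to change.** In protocol section 6.3.1 and SAP section 10:

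1. Extend the 24-month query to date of death, naming the vital-status source, and to admissions in VA-reimbursed community claims, for all randomized participants. Under protocol section 5.7, exclude data after withdrawal for anyone who declines further CDW follow-up.
2. Make this pull part of safety monitoring, whether or not the budget impact analysis goes ahead.
3. Report by arm over 24 months: deaths, participants with at least one admission, total admissions, and participants with death or any admission.
4. Add the 24-month count to the SAP. Version 3.3 (June 2024) predates the protocol version that introduced it (March 2025).
5. Reconcile the two documents on chart review: whether it is limited to the VA, and whether the 21-month review covers everyone or only survey non-completers.

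**Cost.** Wording in two documents and extra fields in a planned query, with no participant contact and no change to the primary analysis. Claims arrive late, so the final pull would have to wait for them, and SAE counts may rise. Admissions not paid for by the VA would still be visible only through self-report or chart review.

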6.3.1. Adverse event monitoring

- Updated adverse expected events to explicitly include death, in alignment with established Data Safety Monitoring Board analysis plan.

Version 2.18 07/02/2024

5.4. Inclusion/Exclusion Criteria & 5.5.2. Primary Outcomes:

- Added details around how weights pulled from the electronic health record are reviewed for suspect or erroneous values.

Version 2.19 03/04/2025

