- Development of weight and OSA associated medical disorders including diabetes, hypertension, liver disease, cardiovascular disease, cerebrovascular disease, arrhythmias, asthma, COPD, clotting problems, and other lung related conditions;
- Development or exacerbation of mental health conditions, the worsening of which is known to be associated with poor sleep, including depression, anxiety, posttraumatic stress disorder, and bipolar disorder.
- Development or exacerbation of eating disorders including binge eating disorder, anorexia nervosa, and bulimia nervosa.
- Development of other conditions associated with unhealthy health behaviors, such as from tobacco and alcohol disorders (e.g., cancer).
- Age related illnesses, such as pneumonia, urinary tract, and skin infections.
- Motor vehicle collision or other accidents arising from excessive sleepiness.
- Death

Upon discovering an unexpected and related SAE, study staff will provide the IRB and DSMB with a report describing the duration (start and stop dates and times), severity, outcome, treatment, and relation to study activity, according to the required timelines. The DSMB may request additional information if it deems additional deliberation is warranted.

For all other events, staff will summarize and report to the DSMB on an annual basis the numbers and types of all AEs by unidentified treatment arms. At their discretion, the DSMB may request unblinded results to determine the nature and extent of effect of the intervention. Should the DSMB make this request, we will maintain blinding of the investigators and the staff involved in follow-up data collection and analysis. If, at any time, the investigators believe they are seeing an unexpected increase in SAEs that is a cause of concern, they will bring this to the attention of the DSMB.

For annual reporting, staff also will provide the quality monitoring report to the DSMB.

At the annual meeting, the DSMB will review AE/SAEs and the quality of data, as well as review study progress and provide objective recommendations, as appropriate, with respect to:

- Determination of any actions to be taken in response to SAEs.
- Reports related to study operations and the quality of the data.
- Consideration of early termination of the study because of treatment safety concerns or inadequate performance.

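### Death is listed without qualifier as an expected event, so read literally a death judged related to study activity need not trigger the individual report to the IRB and DSMB

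*Protocol*

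**What the plan says.** Protocol section 6.3.1 defines seriousness by two outcomes: "We define SAEs as those requiring hospitalization or death". A clinician assesses each adverse event on several separate attributes, among them expectedness, outcome and relation to study activity.

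The section then sets out what counts as expected: "The following are expected adverse events in the POWER population of participants who have obstructive sleep apnea, a high BMI". The items include:

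- "Musculoskeletal symptoms or injury resulting from increased physical activity, including increasing symptoms such as chest discomfort, shortness of breath"
- "Development of weight and OSA associated medical disorders including diabetes, hypertension, liver disease, cardiovascular disease, cerebrovascular disease, arrhythmias"
- "Age related illnesses, such as pneumonia, urinary tract, and skin infections"
- mental health conditions, eating disorders, and accidents caused by sleepiness
- Death, as the last item, with nothing said about cause or relatedness.

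The reporting rule follows the list: "Upon discovering an unexpected and related SAE, study staff will provide the IRB and DSMB with a report". Everything else takes another route: "For all other events, staff will summarize and report to the DSMB on an annual basis". That summary gives counts and kinds of events with the arms masked.

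The entry for Death is deliberate. The protocol's summary of edits for version 2.17 records: "Updated adverse expected events to explicitly include death, in alignment with established Data Safety Monitoring Board analysis plan". SAP section 10 carries the same list, ending in the same unqualified item, but contains no reporting trigger.

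**The concern.** The expected list and the reporting trigger do not fit together. The trigger is meant to bring a possible harm of the intervention promptly to the two bodies that can act on it. It requires the event to be unexpected, and the list makes death, as such, expected. A clinician could judge a death to be caused by the diet or activity programme and still find, on the text, that no individual report is required.

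The list also names harms that a diet and exercise programme could plausibly produce: injury from activity, cardiac and rhythm disorders, and eating disorders. A related admission for one of these also fails the unexpected condition.

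The stake is participant safety and oversight. No endpoint, estimate or sample size is affected. A count in a masked annual table does not do the work of a single-case report, which under section 6.3.1 describes the event's duration, severity, outcome, treatment and relation to study activity.

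**Working it through.** No arithmetic applies, and the plan states no figure to reproduce. The check is to run the rule as written on each type of related event.

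**Inputs, all from Protocol section 6.3.1**

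- Serious = hospitalisation or death.
- Expected = on the list.
- Individual report required = serious AND unexpected AND related.
- Otherwise = annual DSMB summary.

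**Cases, each judged related to study activity**

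| Case | On the list? | Individual report required? |
|---|---|---|
| 1. Death recorded as the event | Yes (Death) | No |
| 2. Listed cause leading to admission | Yes (cause) | No |
| 3. Listed cause leading to death | Yes (cause and outcome) | No |
| 4. Unlisted cause leading to admission, participant survives | No | Yes |
| 5. Unlisted cause leading to death, expectedness judged on the cause | No | Yes, with death reported as the outcome |
| 6. Unlisted cause leading to death, expectedness judged on the fatal outcome | Yes (Death) | No |

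Cases 5 and 6 are the same clinical event under two readings, and the protocol does not choose between them. The separate assessment of outcome, and the requirement that the report describe it, favour the reading in case 5. The bare entry for Death favours case 6. Under case 6 the rule gives a perverse ordering: an unlisted related event that puts a participant in hospital is reported individually, while the same event causing death without an admission is not.

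**Other routes in the same section for cases 1, 2, 3 and 6**

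- Annual summary: it goes to the DSMB, arms masked. The sentence describing it does not mention relatedness and does not name the IRB.
- Investigator alert: it may be raised at any time, but it concerns an unexpected rise in serious events, not a single case.
- DSMB powers: the board may ask for more information, request unblinded results, decide on action after serious events and consider early termination. It needs to know of the case first.
- Hospital admissions by arm: these appear in the final DSMB report, too late to act as an alert.

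Nothing in either document exempts a related death from the list or gives it its own individual report. Within section 6.3.1 the IRB is named only as a recipient of the unexpected-and-related report.

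**The case against.** The strongest reply is that this is an ambiguity and that the rule still works in many cases. Expectedness and outcome are assessed separately, so a sensible clinician would judge the cause and record death as its outcome. That stands in part. A reader might infer that the rule can never fire for a death, or that the share of deaths able to trigger it is zero. The documents do not support this, because case 5 is open on the text. Cases 1 and 3 remain blocked, however, and the choice between cases 5 and 6 is left to the assessor.

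A reader might also infer that most causes of hospitalisation are covered by the list. That cannot be verified. The documents give no admissions by cause, hospitalisation itself is not listed, and several items carry qualifiers: accidents must arise from sleepiness, and medical disorders must be associated with weight or OSA. What can be said is that the list is broad.

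Nor do the documents support a fixed delay of 12 months. The DSMB reviews the study at least annually, so a year is not a set interval. Events are gathered mainly by surveys at 12 and 21 months and by chart review, so much of any delay may come before discovery, and rewording the trigger would not remove it.

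Finally, the listing was aligned with DSMB documentation, a DSMB charter exists, and reports are to follow required timelines that come from outside the protocol. These sources may separately require prompt notice of deaths. They are not in the documents, so this can be neither confirmed nor excluded. It is a reason for moderate confidence, but it does not reconcile the list with the trigger in the protocol's own text. That the intervention is described as consistent with guideline care (SAP section 5) limits how many cases to expect, not how one should be handled.

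**Conclusion.** The point holds as an inconsistency between the expected list and the reporting rule. As written, a death recorded as the event and judged related need not be reported individually to the IRB and DSMB. The same is true of a related admission or death from a listed cause. A related death from an unlisted cause may or may not be reported, depending on a reading that the protocol leaves open.

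The size cannot be expressed as a number: the documents give no expected deaths, admissions by cause or relatedness rates. In a trial of this kind the affected cases are probably few, but they are the ones for which the rule matters most.

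The conclusion assumes that the list defines expectedness for the trigger, as the shared term in section 6.3.1 implies, and that no external rule already requires the individual report.

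**What to change.** In Protocol section 6.3.1, next to the reporting trigger, state two things:

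1. Expectedness is judged on the underlying event, not on the fatal outcome.
2. Any death judged related to study activity is reported individually to the IRB and DSMB, even if death or its cause is on the expected list.

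Keep the list for the annual tabulation. In SAP section 10, which has no trigger to amend, add only a matching qualifier to Death or a cross-reference to the protocol rule.

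Reporting every death regardless of relatedness, or dropping the unexpected condition for all serious events, would go further than this defect requires. Those are debatable choices for the sponsor and the DSMB. Related admissions for listed causes would remain in the annual summary under this fix; the sponsor should confirm that this is intended.

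The cost is one or two sentences, a notice to the IRB and DSMB, and a few extra single-case reports. Sample size, analysis and participant burden do not change.
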